12.3.4.2 Inferential Analysis of PK Parameters

Comparison of PK between Ethnic Groups

In order to compare the PK of rhPTH(1-84) between subjects of Japanese descent and matched non-Hispanic, Caucasian subjects, the differences of log-transformed PK parameters from the rhPTH(1-84) 100 μ g dose will be examined between the two ethnic groups using Welch's t-test with Satterthwaite's approximation to the degrees of freedom. The difference between the two means will be back transformed to provide an estimate for the geometric mean ratio and its 90% confidence interval (CI). The following PK parameters will be evaluated using this test: C_{max} and AUC_{last} based on original concentration, baseline-adjusted C_{max} , AUC_{last} , AUC_{0-inf} .

For C_{max} , AUC_{last} (original and baseline-adjusted) and AUC_{0-inf} (baseline-adjusted), Forest plots of geometric mean ratios (two-sided 90% CI) between Japanese cohort at 100 μ g vs Non-Japanese cohort at 100 μ g will be generated.

In addition, same Welch's t-test will be applied to compare the PK parameters between different doses and ethnic groups. The log-transformed dose-normalized AUC_{last} and C_{max} will be examined between the Japanese cohort at 50 μ g dose and the Non-Japanese cohort at 100 μ g as well as between the Japanese cohort at 25 μ g and the Non-Japanese cohort at 100 μ g. The geometric mean ratio estimates and their 90% CI will be provided from the model for each comparison.

Evaluation of Dose Proportionality (Exploratory)

Dose proportionality of baseline-adjusted PK parameters, will be examined for the Japanese subjects. Dose proportionality will be assessed for baseline-adjusted C_{max} , AUC_{last} , and

$AUC_{0-\infty}$, using the power model. The power model assumes a linear relationship between the natural log transformed parameter and the natural log transformed dose.

$$\ln(\text{Parameter}_{ijk}) = \alpha + \beta \times \ln(\text{Dose in } \mu\text{g}) + \pi_j + \gamma_i + \xi_{k(i)} + \varepsilon_{ijk} \quad (\text{Patterson and Jones, 2006})$$

Where α is the intercept, β is the slope, π_j and γ_i identify the period j of sequence i , $\xi_{k(i)}$ is the random-intercept accounting for each subject within sequence as their own control, and ε_{ijk} denotes within-subject error. Dose proportionality will be assessed by estimating mean slope with the corresponding two-sided 90% confidence interval (CI) from the power model. The estimate and 90% confidence interval for the slope will be presented.

The example SAS code for the above model could be:

```
proc mixed method = reml data=ADPP ;
  class subject sequence period ;
  model lnauc = sequence period lndose / s ddfm = kenwardroger cl alpha = .1 ;
  random intercept/ subject = subject (sequence) ;
run ;
```

In addition, a simple regression model will be used to plot the relationship between these three above baseline-adjusted PK parameters and dose for Japanese subjects.

$$\ln(\text{Parameter}) = \text{intercept} + \text{slope} \times \ln(\text{Dose in } \mu\text{g}) + \text{residual}$$

Plots of observed geometric mean and observed individual values of baseline-adjusted PK parameters C_{\max} , AUC_{last} and $AUC_{0-\infty}$ vs dose in Japanese subjects will be generated. The regression line along with the formula and r^2 will be presented in the same plot with both axes on log scale.

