2. STUDY DESIGN

2.1 General Study Design

This study is a Phase 1, open-label, randomized, cross-over, single-center study to evaluate the PK and PD profiles and safety and tolerability of rhPTH(1-84) administered in healthy adult volunteer subjects of Japanese descent and matched non-Hispanic, Caucasian, healthy adult volunteer subjects. The non-Hispanic, Caucasian volunteers will receive a single dose of 100 μ g rhPTH(1-84). The Japanese subjects will receive 3 single doses of rhPTH(1-84). On Day 1 the subjects of Japanese descent will receive a single SC injection of 100 μ g. On Days 4 and 7 the subjects of Japanese descent will be randomized to receive a single SC injection of either 25 μ g or 50 μ g such that all of these subjects are exposed to the 3 dose strengths over a 7-day period to further characterize the PK profile in that group. A total of 24 subjects will be enrolled: 12 non-Hispanic, Caucasian subjects and 12 subjects of Japanese descent (1:1 male: female). Non-Hispanic, Caucasian subjects will be matched to Japanese subjects based on sex, age (± 7 years), and body mass index ($\pm 15\%$).

All subjects will receive a single dose of 100 μ g rhPTH(1-84) administered by SC injection in the mid-thigh with the Haselmeier injector pen on Day 1. In addition, the subjects of Japanese descent will also receive single dose injections of 25 μ g and 50 μ g rhPTH(1-84) administered by SC injection in the mid-thigh to characterize the PK profile over a range of doses. There will be a minimum of 72 hours (maximum 73 hours) washout between doses for the volunteers of Japanese descent. The study duration will comprise of a 28-day screening period, 1 treatment period for the non-Hispanic, Caucasian group (Days 1 and 2); 1 treatment period for the volunteers of Japanese descent (Days 1-8), and a follow-up visit (30 ± 2 days) after the last dose of investigation drug is administered for all subjects. The total number of nights subjects will be expected to stay at the clinical research center (CRC) is 2 for the non-Hispanic, Caucasian group and 8 for the volunteers of Japanese descent. The maximal total duration of study participation is 62 days for a non-Hispanic, Caucasian subject and 68 days for the volunteers of Japanese descent, if the maximum screening, treatment and follow-up visit durations are used.

Screening will occur within 28 days of the first dose. Subjects will be admitted to the CRC on Day -1.

Treatment Period:

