3.2 Secondary Objectives

- To assess the dose proportionality of the selected PK parameters of rhPTH(1-84) in healthy adult volunteer subjects of Japanese descent when exposed to single SC doses of rhPTH(1-84) at 25 μ g, 50 μ g, and 100 μ g.
- To compare the PD profile (serum calcium and phosphate concentration levels vs time) of a 100 μ g SC injection of rhPTH(1-84) in healthy adult volunteer subjects of Japanese descent and matched, non- Hispanic, healthy, adult Caucasian, subjects.
- To assess the PD profile (serum calcium and phosphate concentration levels vs time) of a 25 μ g and 50 μ g SC injection of rhPTH(1-84) in healthy adult volunteer subjects of Japanese descent.
- To assess the safety and tolerability of single SC doses of 25 μ g, 50 μ g, and 100 μ g of rhPTH(1-84) in healthy adult volunteer subjects of Japanese descent.
- To evaluate the safety and tolerability of a 100 μ g SC injection of rhPTH(1-84) in matched, non-Hispanic, healthy, adult volunteer Caucasian subjects.

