12.3.2 Baseline-adjusted PTH Concentration Data

Baseline-adjusted PTH concentrations are to be calculated by subtracting baseline endogenous PTH from the original PTH concentrations. Such baseline adjustment is subject- and dose-specific. For each subject, baseline is defined for each dosing period as follows: the baseline for Day 1 dosing is defined as the average predose concentration on Day 1 (average of predose 1 and predose 2 PTH concentrations); for subjects of Japanese descent the baseline for Day 4 dosing is defined as the average predose concentration on Day 4 (average of predose 1 and predose 2 PTH concentrations); the baseline for Day 7 dosing is defined as the average predose concentration on Day 7 (average of predose 1 and predose 2 PTH concentrations). If the baseline-adjusted PTH concentration gives a negative value, then the baseline-adjusted PTH concentration should be set to zero. In the terminal log-linear phase, if two consecutive baseline-adjusted PTH concentrations give negative values, then all the subsequent values will be set to zero.

Individual baseline-adjusted PTH concentrations will be listed and summarized by ethnic group and dose as in section 12.3.1. Individual plots and mean plots will be generated in the same way as described in section 12.3.1 but using the baseline-adjusted PTH concentrations. If the baseline-adjusted PTH concentration is zero, it will be presented as missing on the semi-log scale.

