12.3.3 Pharmacokinetic Parameters

The pharmacokinetic analysis will be conducted by using WinNonlin Phoenix version 6.3 or higher (Pharsight Corporation, Mountain View, California, USA). Pharmacokinetic parameters will be determined from the plasma PTH concentration-time data by non-compartmental analysis. Both original and baseline-adjusted PTH concentrations will be used to compute all the PK parameters respectively.

The pharmacokinetic parameters will include, but may not be limited to:

- C_{max} : Maximum observed concentration, to be reported in the unit of pg/mL (both original and baseline-adjusted PTH)
- t_{max} : Time of maximum observed concentration sampled during a dosing interval, to be reported in the unit of hour (both original and baseline-adjusted PTH)
- AUC_{last} : Area under the curve from the time of dosing to the last measurable concentration. Calculated using the linear up/log down method, to be reported in the unit of pg.hr/mL (both original and baseline-adjusted PTH)
- AUC_{0-inf} : Area under the curve extrapolated to infinity calculated as $AUC_{last} + C_{last}/\lambda_z$. Calculated using the linear up/log down method, to be reported in the unit of pg.hr/mL (for baseline-adjusted PTH only)
- %AUC extrapolated: % of AUC extrapolated from the last measurable concentration to infinity over $AUC(0-inf)$ (for baseline-adjusted PTH only)
- λ_z : Elimination rate constant associated with the terminal (log-linear) portion of the curve. The log-linear portion of the curve must contain at least three points after T_{max} and have an r^2 value ≥ 0.8 (for baseline-adjusted PTH only)
- $t_{1/2}$: Terminal half-life, calculated as $0.693/\lambda_z$ (for baseline-adjusted PTH only)
- CL/F: Apparent total body clearance, calculated as Dose/ AUC_{0-inf} (for baseline-adjusted PTH only)
- Vd_z/F : Apparent volume of distribution, calculated as Dose/ $AUC_{0-inf} * \lambda_z$ (for baseline-adjusted PTH only)

All PK parameter calculations will be performed using actual sampling times calculated relative to the day of rhPTH(1-84) administration. The PK parameters λ_z , $t_{1/2}$, AUC_{0-inf} , CL/F, and Vd_z/F will not be calculated for subjects with PTH concentration-time profiles (baseline-adjusted) that do not exhibit a terminal log-linear phase, or if %AUC extrapolated $> 20\%$.

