17. CHANGES TO ANALYSES SPECIFIED IN PROTOCOL

Section 9.8.1.1 (Statistical Analysis of Pharmacokinetic Parameters) of the protocol states that:

Dose proportionality of PK parameters will also be examined for the Japanese subjects. Dose proportionality will be assessed for C_{max} and AUC (AUC_{last}) using the power model. The power model assumes a linear relationship between the natural log transformed parameter and the natural log transformed dose.

$$\ln(\text{Parameter}) = \alpha + \beta \times \ln(\text{Dose}) + \text{Random error}$$

In order to compare the PKs of rhPTH(1-84) between subjects of Japanese descent and matched non-Hispanic, Caucasian subjects, the differences of log-transformed PK parameters from the rhPTH(1-84) 100 μ g dose will be examined between groups using an analysis of variance model.

However, to take account of the different sequences, the dose proportionality of PK parameters will be assessed by the power model with more factors:

$$\ln(\text{Parameter}_{ijk}) = \alpha + \beta \times \ln(\text{Dose in } \mu\text{g}) + \pi_j + \gamma_k + \xi_{k(i)} + \varepsilon_{ijk} \quad (\text{Patterson and Jones, 2006})$$

Where α is the intercept, β is the slope, π_j and γ_i identify the period j of sequence i , $\xi_{k(i)}$ is the random-intercept accounting for each subject within sequence as their own control, and ε_{ijk} denotes within-subject error. Dose proportionality will be assessed by estimating mean slope with the corresponding two-sided 90% confidence interval (CI) from the power model.

For the comparison of PKs between subjects of Japanese descent and matched non-Hispanic, Caucasian subjects, the differences of log-transformed PK parameters from the rhPTH(1-84) 100 μ g dose will be examined between the two ethnic groups using Welch's t-test with Satterthwaite's approximation to the degrees of freedom, rather than by ANOVA as stated in the protocol. The reason for this method of comparison is that the variance in the two ethnic groups is not expected to be the same.

Table 1 Schedule of Assessments from protocol states that randomization takes place on Day 4 for subjects of Japanese descent. It is changed to be on Day 1 in Table 1 in SAP.

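### The SAP power model's period effect absorbs the 100 µg dose, so its dose-proportionality slope covers only 25 to 50 µg

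*SAP*

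**What the plan says.** SAP 3.2 lists as a secondary objective "To assess the dose proportionality of the selected PK parameters of rhPTH(1-84) in healthy adult volunteer subjects of Japanese descent" given 25, 50 and 100 µg.

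The dosing design is in SAP 2.1 and 2.2: "On Day 1 the subjects of Japanese descent will receive a single SC injection of" 100 µg. The 1:1 randomisation decides only whether 25 µg is given on Day 4 and 50 µg on Day 7, or the reverse.

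SAP 12.3.2 treats Days 1, 4 and 7 as separate dosing periods ("For each subject, baseline is defined for each dosing period as follows").

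The power model in SAP 12.3.4.2 has terms for sequence, period and ln(dose), with a random subject intercept. The example code puts period in the CLASS statement and fits "model lnauc = sequence period lndose / s ddfm = kenwardroger cl alpha = .1". Proportionality is assessed from the slope and its two-sided 90% CI.

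The power model in Protocol 9.8.1.1 has only an intercept, ln(dose) and error, with a 95% CI. SAP 17 explains the change thus: "to take account of the different sequences, the dose proportionality of PK parameters will be assessed by the power model with more factors". It does not discuss how period relates to dose.

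SAP 12.3.4.2 adds a second output: "a simple regression model will be used to plot the relationship between these three above baseline-adjusted PK parameters and dose for Japanese subjects". The line, its formula and r² are shown on the plot, but no CI is planned.

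**The concern.** A three-level period factor has one free parameter for Day 1. All Day 1 records, and only those, are at 100 µg. That parameter can therefore fit the mean at 100 µg exactly, wherever it lies, which leaves nothing at 100 µg for the slope to explain.

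The only slope with a planned CI would then answer the secondary objective over half of the range on the log scale (25 to 50 µg). Neither the text nor the title of Table 2.1.10 says so. A reader could see a slope near 1 in the table beside a plotted line with a clearly different slope and have no explanation for the disagreement.

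**Working it through.** **Inputs.** There are 12 Japanese subjects (SAP 2.1), two sequences taken as 6:6 (SAP 2.2: 100-25-50 and 100-50-25), three periods, and the SAP 12.3.4.2 model. That gives 36 records. The documents give no within-subject CV, so 15%, 25% and 35% are assumptions used only for CI widths. The plan states no precision for the slope to reproduce; its one checkable pair, alpha = .1 in the code and 90% in the text, agrees.

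**1. Aliasing.** The Day 1 and 100 µg indicators are identical in all 36 records. The fixed-effects matrix (intercept, sequence, two period terms, ln dose) has rank 5. Adding a column for a departure at 100 µg leaves the rank at 5, so such a departure is fully aliased with period.

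**2. Weights in the slope.** Summed over records at 25 / 50 / 100 µg, where 1.443 = 1/ln 2:
- SAP model: −1.443 / +1.443 / 0. Each single 100 µg record has weight zero, so these records inform only the residual variance.
- Subject effect with no period, or with a Day 7 versus Day 4 contrast: −0.721 / 0 / +0.721.

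**3. Precision.** SE = σw/√SSx, where SSx is the sum of squares of ln(dose) left after the other terms.
- SAP model: SSx = 12 × 2 × (ln 2 / 2)² = 2.883, so SE = 0.589σw.
- No period, or the contrast: SSx = 12 × 2 × (ln 2)² = 11.531, so SE = 0.2945σw.
- The ratio is 2.0.
- Against the nominal SE of the protocol's model, which has no subject effect, the ratio is 2/√(1 + r²), with r the between/within SD ratio: 2.00, 1.41 and 0.89 at r = 0, 1 and 2.

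Half-width = t × SE, with σw = √ln(1 + CV²) and 21 df (SAP) or 22 df (contrast). At 25% CV, σw = 0.246, and the SAP 90% half-width is 1.721 × 0.589 × 0.246 = 0.25.

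| Assumed CV | SAP 90% | Contrast 90% | SAP 95% | Contrast 95% |
|---|---|---|---|---|
| 15% | ±0.15 | ±0.08 | ±0.18 | ±0.09 |
| 25% | ±0.25 | ±0.12 | ±0.30 | ±0.15 |
| 35% | ±0.34 | ±0.17 | ±0.42 | ±0.21 |

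**4. Response to a departure at 100 µg.** Let exposure at 100 µg be f times proportional. The expected SAP slope is 1.00 for every f. The three-dose slope is 1 + ln f/(2 ln 2):
- f = 1.4: 1 + 0.336/1.386 = 1.24.
- f = 0.7: 1 − 0.357/1.386 = 0.74.

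REML fits to one simulated data set (true slope 1, CV 25%), with the 100 µg values multiplied by 1 / 1.4 / 0.7, behaved the same way:
- SAP model: 1.036 / 1.036 / 1.036.
- Contrast model and simple regression: 1.004 / 1.246 / 0.746.

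**5. Missing values.** SAP 12.3.3 says AUC0-inf and related parameters "will not be calculated for subjects with PTH concentration-time profiles (baseline-adjusted) that do not exhibit a terminal log-linear phase", so gaps are possible. With three of 12 subjects lacking a 25 µg value, 100 µg records regain 4% / 8% / 10% of the absolute weight (between/within SD ratio 0.5 / 1 / 2), or 8% / 11% / 13% if all three are in one sequence. Those weights still sum to zero, because an unbiased slope must be unaffected by the Day 1 parameter. A common departure at 100 µg still cannot move the slope: in the simulated data with three values missing, the SAP slope was 1.095 in all three cases, against 1.029 / 1.289 / 0.755 for the contrast.

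**The case against.** **Departures at 100 µg can be seen elsewhere.** SAP 12.3.4.1 plans dose-normalised summaries by dose, with 95% CIs of the geometric means, and plots against dose. SAP 12.3.4.2 compares dose-normalised exposure at 25 and 50 µg with the Caucasian 100 µg group. With complete data the plotted regression has the same slope as the proposed contrast model. All this stands, and a large departure would probably be noticed. None of it gives a CI for a three-dose slope within subjects, and none tells the reader that the tabulated slope excludes 100 µg.

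**The analysis is headed exploratory, and no acceptance range is set.** True, and this limits the consequence. It still serves a stated secondary objective over 25 to 100 µg.

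**The planned slope is protected against a Day 1 effect, and the replacement is not.** This is the strongest point. The fixed Day 1 dose is the root cause, and no model can separate a Day 1 effect from a departure at 100 µg. A pure Day 1 shift of 10% (20%) would move the contrast slope by 0.07 (0.13), and 0.13 is close to its whole 95% half-width at 25% CV (0.15). The halved SE depends on assuming no such shift. That is a reason to report both models, not to report only the one that cannot see 100 µg.

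**The code is only an example, and the number of period levels is not stated.** The model equation in SAP 12.3.4.2 and SAP 17 also contains period, and SAP 12.3.2 defines dosing periods by Days 1, 4 and 7. Pooling Day 1 with Day 4 would bring 100 µg back (summed weight about +0.67), but the SAP does not specify it. Leaving period missing on Day 1 would drop those records, with the same conclusion.

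**Proportionality is already known.** Protocol 3.2 reports it over this range in western studies. Whether it holds in Japanese subjects is what this study sets out to assess.

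**Conclusion.** The concern holds and should be fixed. With period fitted as three dosing days, the aliasing is algebraic and does not depend on any variance. With complete data the slope is the 25 versus 50 µg crossover contrast divided by ln 2; with missing values it still cannot respond to a common departure at 100 µg of any size. The doubling of the SE assumes complete, balanced data and, for the comparator, no Day 1 shift. The CI widths rest on assumed CVs, and the 40% and 30% departures are illustrations.

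A separate, smaller discrepancy is the CI level: 95% in Protocol 9.8.1.1 and 90% in the SAP. SAP 17 states 90% without a reason, although the protocol's summary of changes explains a deliberate move from 90% to 95%. The conclusion above does not rely on this.

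**What to change.** In SAP 12.3.4.2 and 17:

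- For the 25 to 100 µg slope, replace the three-level period factor with a Day 7 versus Day 4 contrast (0 on Day 1, −0.5 on Day 4, +0.5 on Day 7). Keep sequence and the random subject intercept. Dropping period is an acceptable alternative; the two coincide with balanced complete data but can differ slightly otherwise, so the SAP should name one.
- State that this assumes no shift between Day 1 and the later days, which the design cannot separate from a departure at 100 µg. The 72-hour washout, the 1 to 2 hour half-life (Protocol 3.2) and the per-period baselines support the assumption for carry-over and baseline drift, but not for other day effects.
- Keep the planned full-period model as a sensitivity analysis labelled 25 to 50 µg only, and put the dose range in the title of Table 2.1.10.
- Separately, use the protocol's 95% CI for the slope or give the reason for 90% in SAP 17.

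The cost is one line of SAS code, one extra table row, a title edit and a stated assumption, with no new data. The main slope would then carry any Day 1 effect, which is why the full-period model stays. At 25% CV, going from the SAP's 90% interval to a 95% interval on the revised model changes the half-width from ±0.25 to ±0.15, provided the no-shift assumption holds.

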12.4 Pharmacodynamic Methods

All summaries and analyses of the PD data will be based on the Pharmacodynamic Set. After database lock, a visual inspection of concentration-time profiles and PD parameters will be performed by PRA to determine dataset integrity and potential outliers. Descriptive statistics of PD parameters may be calculated with and without subjects with potential outlier data. Subjects with potential outlier data will be reviewed by Shire for inclusion/exclusion from the descriptive statistics on a case-by-case basis.

12.4.1 Original Pharmacodynamic Data

Blood samples for PD analysis will be collected at Predose 2 (within 30 min prior to dose administration), 4, 8, 12 and 24 hours after dose administration of rhPTH(1-84) for the determination of concentrations of serum calcium (uncorrected [total] and corrected for serum albumin levels), phosphate. Serum calcium will be corrected for serum albumin levels using the following equation:

Corrected calcium (mmol/L) = serum calcium (mmol/L) + 0.02 (40 - serum albumin (g/L))
(Parent X, 2009)

The serum calcium-phosphate product (using albumin-corrected calcium) will also be determined. This is calculated as serum calcium concentration (albumin-corrected) x serum phosphate concentration.

Individual original concentrations of serum total calcium, albumin-corrected calcium, phosphate and calcium-phosphate product will be listed and summarized with descriptive statistics (number, arithmetic mean, SD, CV%, median, minimum, maximum) by ethnic group, dose and time point.

Figures of individual original concentration-time profiles and mean (\pm SD) will be generated on linear scale for serum total calcium, albumin-corrected calcium, phosphate and calcium-phosphate product by ethnic group and dose. The mean plots will be created for the original concentrations of the above four PD markers by overlaying the mean values for each ethnic group and dose on the same figure.

